4.3 Inclusion of Women and Minorities

Both men and women and members of all races and ethnic groups are eligible for this trial. The University of Arizona Cancer Center has faculty and staff who are dedicated to conduct outreach into minority populations. These resources will be available to this recruitment effort.

4.4 Recruitment and Retention Plan

Study participants will be recruited from the greater Tucson area by word-of-mouth, advertisement in local newspapers and flyers posted around campus and in gathering places of minority populations, and through use of the local Craigslist and social media. Study personnel will promote retention/adherence with regular contact with study subjects. The study team is committed to provide a friendly and comfortable study setting for participants from initial contact through the completion of their activities. Wherever possible, flexibility will be built into the study schedule to promote compliance. Recruitment and retention efforts will be evaluated routinely by the study personnel and modified as necessary to promote rapid accrual and to assure 100% retention of participants.

5. AGENT ADMINISTRATION

Intervention will be administered on an outpatient basis. Reported adverse events (AEs) and potential risks are described in Section 6.2.

5.1 Dose Regimen and Dose Groups

- The study agents are aspirin and zileuton.
- Participants will be randomly assigned to one of the following treatment groups:
 - Aspirin 81 mg QD + zileuton (Zyflo CR) 2 x 600 mg BID
 - Double placebo (Aspirin placebo 1 cap QD + Zileuton placebo 2 tabs BID)
- Duration of treatment is 12 weeks.

5.2 Study Agent Administration

- Participants will receive a supply of ASA + zileuton or double placebo from the study coordinator.
- Participants will be instructed to take one capsule of ASA/placebo QD and 2 tablets Zileuton/placebo BID.
- Participants will be instructed to take the study agents at the same time each day.
- Participants will be instructed to take the ASA/placebo in the morning with 8 oz. of water and with food to lessen stomach irritation.
- Participants will be instructed to take the zileuton/placebo within one hour after the morning and evening meals. The ASA/placebo and morning dose of zileuton/placebo may be taken simultaneously.

5.3 Wash-out Procedures

Participants who are using ASA or other NSAIDs within the preceding 2 weeks will undergo a minimum of 4 weeks washout period prior to receiving study treatment.

5.4 Contraindications

Participants should refrain from using more than 2 alcoholic beverages per day for the duration of the trial.

5.5 Concomitant Medications

Participants are required to refrain from taking non-study aspirin or other NSAIDs for the duration of the trial. Participants are required to refrain from taking non-study zileuton or other leukotriene antagonists. Participants are required to refrain from the use of anti-coagulant or anti-platelet medications for the duration of the trial. Participants are required to refrain from the use of medications that are known to interact with zileuton, including theophylline, warfarin, and propranolol. Participants should refrain from the regular use of glucocorticoids (systemic, topical or nasal) or OTC nasal sprays.

All medications (prescription and over-the-counter), vitamin and mineral supplements, and/or herbs taken by the participant will be documented on the concomitant medication CRF and will include: 1) start and stop date, dose, and indication. Medications taken for a procedure (*e.g.*, biopsy) should also be included.

5.6 Dose Modification

For participants who demonstrate Grade 1 dyspepsia, a proton pump inhibitor (PPI) will be instituted promptly for relief of discomfort and subject may continue taking study drugs. For Grade 2 dyspepsia lasting for more than three days despite use of PPI, both study drugs will be held. If symptoms resolve within 2 weeks, the subject may resume study drugs at the same dose while using the PPI (PPI can be used at BID). For a second Grade 2 dyspepsia despite use of PPI, both study drugs will be permanently withdrawn and the participant followed for resolution of the adverse event(s). For any evidence of GI bleeding, the study drugs will be stopped promptly and the participant followed for resolution of the adverse event(s).

For other Grade 1 adverse events, no dose modification will be made. For other Grade 2 adverse events definitely, probably or possibly related to study drugs persisting for more than three days, both study drugs will be held. Both study drugs will be reintroduced at the same dose if the adverse event resolves to Grade 1 or below within 2 weeks. If the Grade 2 event does not resolve to Grade 1 or below within 2 weeks, both study drugs will be permanently withdrawn and the participant followed for resolution of the adverse event. If the Grade 2 adverse event recurs following reinstatement of the study agents and is considered definitely, probably or possibly related to study drugs, both study drugs will be permanently withdrawn and the participant followed for resolution of the adverse event(s). If the Grade 2 adverse event is not considered related to study drugs, both study drugs may be held and reintroduced within two weeks at the discretion of the study physician.

For any Grade 3 adverse events regardless of relationship to study drugs, both study drugs will be held. For Grade 3 events unrelated to study drugs, both study drugs may be resumed within two weeks at the discretion of the study physician. Grade 3 events possibly or probably related to study drugs, and Grade 4 events regardless of relationship to study drugs, will result in permanent withdrawal of both study drugs. Participants will be followed for resolution of adverse events. Where possible and appropriate, participants withdrawn early will be encouraged to return for sample collection and clinical labs for safety.

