11.1.4 Assessment of relationship of AE to treatment

The possibility that the adverse event is related to study agent will be classified as one of the following: not related, unlikely, possible, probable, definite.

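### Does the Grade 3 rule in section 5.6 leave a definitely related event without a safeguard because its withdrawal sentence omits that category?

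*Combined protocol and SAP*

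**What the plan says.** Section 11.1.4 requires the relationship of each adverse event to study agent to be "classified as one of the following: not related, unlikely, possible, probable, definite".

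Section 5.6 handles Grade 3 events in three sentences:

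- First step, for all events: "For any Grade 3 adverse events regardless of relationship to study drugs, both study drugs will be held".
- Route back to treatment: "For Grade 3 events unrelated to study drugs, both study drugs may be resumed within two weeks at the discretion of the study physician".
- Permanent withdrawal: "Grade 3 events possibly or probably related to study drugs, and Grade 4 events regardless of relationship to study drugs".

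For Grade 2 events other than dyspepsia, the same section is fuller. The hold applies "For other Grade 2 adverse events definitely, probably or possibly related to study drugs persisting for more than three days", and the recurrence rule applies if the event "is considered definitely, probably or possibly related to study drugs, both study drugs will be permanently withdrawn".

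Three other places bear on the point. Section 5.6 has participants followed until adverse events resolve, and encourages those withdrawn early to return for samples and safety labs. Section 8.3 lists an adverse event as a reason for going off agent and, where possible, continues endpoint collection afterwards. Section 13.8 assesses response in everyone who has endpoint data.

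**The concern.** The Grade 2 rules spell out all three related categories, and do so twice, so the protocol does not habitually fold definite into probable. The Grade 3 withdrawal sentence then names only two of the three. Taken literally, a severe event about whose cause the physician has no doubt is missing from the list that triggers permanent withdrawal, while a severe event that is only possibly related is on it. The rule for the more severe grade looks less complete than the rule for the milder one.

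The setting makes this worth checking. Section 6.2.3 reports no combination studies of aspirin and zileuton and no published human safety data on their joint use in healthy individuals, and it does not entirely exclude additive hepatic toxicity. If the omission allowed re-exposure after a definitely related Grade 3 event, it would be a fault in a participant-protection rule. If different physicians filled it in differently, reasons for stopping drug might also be recorded inconsistently.

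**Working it through.** No figure is involved. The check maps each attribution level in 11.1.4 to the sentences in 5.6.

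| Attribution (11.1.4) | Grade 3: first step | Grade 3: what follows | Named in the general Grade 2 rules? |
|---|---|---|---|
| Not related | Both drugs held | May be resumed within two weeks, physician's discretion | Yes |
| Unlikely | Both drugs held | Not named; may be read with unrelated | No |
| Possible | Both drugs held | Permanent withdrawal | Yes |
| Probable | Both drugs held | Permanent withdrawal | Yes |
| Definite | Both drugs held | Not named | Yes |

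**Count.** All 5 levels have a stated first action at Grade 3. Three of the 5 have an explicit final step (not related, possible, probable), which leaves 5 − 3 = 2 without one.

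**Definite.** The first sentence takes the participant off both drugs. The resumption sentence does not reach this event, because it is limited to unrelated events. No other sentence in 5.6 offers a return to treatment after a Grade 3 event. Under the text as written, the participant stays off drug. The missing item is the label: continuing hold or permanent withdrawal.

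**Unlikely.** If this level is read with unrelated, resumption is at the physician's discretion. If it is not, the hold simply continues. Section 11.2.3 gives serious events that are unrelated and those unlikely to be related the same minimum follow-up, which supports reading them together, although it names them separately. The Grade 2 rules do not name this level either, so it is no evidence that Grade 2 is the more complete rule.

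**Comparison with Grade 2.** The general Grade 2 hold for related events starts only once the event has lasted more than three days, and it allows reintroduction if the event settles in time. The Grade 3 hold has no such waiting period and ignores attribution. The order of protection is therefore not reversed by the missing word.

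**Analysis.** A participant left on hold and one formally withdrawn take the same number of doses from that point, so the pill count behind the 80% compliance rule (5.7.1, 13.6) does not depend on the label. Under 8.3 the reason for stopping is an adverse event in either case. Under 13.8 both are assessed for response if they have endpoint data. The two-sample t test in 13.4 uses change from baseline and makes no use of the distinction.

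**The case for a change.** The best argument for acting is that a hold and a permanent withdrawal are different statuses, and a protocol should say which one each attribution level leads to. The gap is not closed elsewhere: 8.3 only permits stopping, without a threshold of grade or attribution; the gastrointestinal bleeding rule covers that event alone; and the Grade 4 clause covers Grade 4 alone. Drug-attributable events are foreseeable. Section 6.2.2 reports ALT at three times the normal limits in 5 of 199 patients on zileuton against 1 of 198 on placebo in the 12-week study. Correcting the wording would cost almost nothing.

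The textual part of this stands: the word is missing, no other section supplies it, and it is not a redaction or an extraction fault. The inference to a safety risk does not stand, because the text takes the participant off drug and offers return only for unrelated events. The attrition argument has no event rate or count behind it, and the protocol continues endpoint collection off drug where possible. Low cost makes an edit convenient, but it does not show that the plan as it stands would be applied wrongly.

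**Conclusion.** The omission is real, but it is a clerical slip with no practical consequence that can be shown. One attribution level of five, definite, lacks a stated final step after a Grade 3 hold. A second, unlikely, lacks one only on the stricter reading. Neither gap authorises re-exposure, and neither alters the primary or secondary comparisons.

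This rests on two assumptions. The first is that resumption after a Grade 3 hold is allowed only where 5.6 says so, which is the ordinary reading of a rule that holds for all events and then names one exception. The second is that physicians settle the formal status after the hold sensibly and record an adverse event as the reason for stopping.

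No change to the plan is needed on statistical grounds. As an editorial matter, the Grade 3 sentences must be reconciled with the Grade 2 sentences and with the five levels in 11.1.4 when the section is next revised. The clinical content is for the sponsor and investigators to decide.

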5.7 Adherence/Compliance

- 5.7.1 Participants will be considered compliant for statistical analysis if they have taken $\geq 80\%$ of their assigned study doses based on count of return pills.
- 5.7.2 The primary measure of compliance includes pill count. The secondary measure of compliance will be the Intake Calendar. Plasma levels of study agents and metabolites can also be used to confirm compliance.

6. PHARMACEUTICAL INFORMATION

6.1 Study Agents

6.1.1 Aspirin

A marketed 81 mg aspirin capsule will be used in this study. Aspirin is an odorless, white, needle-like crystalline or powdery substance. When exposed to moisture, aspirin hydrolyzes into salicylic and acetic acids, and gives off a vinegary odor. It is highly lipid soluble and slightly soluble in water. The capsule contains 81 mg aspirin and the following excipients: carnauba wax, cellulose, D&C Yellow #10 Aluminum Lake, FD&C Yellow #6 Aluminum Lake, hypromellose, iron oxides, methacrylic acid copolymer, polysorbate 80, propylene glycol, shellac, sodium lauryl sulfate, starch, titanium dioxide, triacetin.

6.1.2 Zileuton (IND #64362, IND Sponsor: NCI, DCP)

Zileuton (\pm -1-(1-benzo[b]thien-2-ylethyl-1-hydroxyurea) is an FDA-approved orally active drug indicated for the prophylaxis and long-term treatment of asthma in adults and children aged 12 years or older. It inhibits 5-lipoxygenase (5-LOX) and production of pro-inflammatory leukotrienes LTB₄, LTC₄, LTD₄, and LTE₄, producing moderate airway function improvement. Both the *R*(+) and *S*(-) enantiomers in the racemic mixture are pharmacologically active inhibitors *in vitro* and *in vivo*. The zileuton immediate-release tablet formulation (Zyflo R Filmtabs) was discontinued in March 2008. An improved extended-release formulation of zileuton (Zyflo CR) was approved by FDA in 2007 [Cornerstone Therapeutics, Inc., 2011]. The recommended dose in adults is 2 x 600 mg bid, taken one hour after morning and evening meals.

Zileuton (Zyflo CR™) 600 mg extended-release tablets are triple-layered tablets comprised of an immediate-release layer, a middle (barrier) layer, and an extended-release layer. Each tablet contains 600 mg zileuton and the following inactive ingredients: crospovidone, ferric oxide, glyceryl behenate, hydroxypropyl cellulose, hypromellose, magnesium stearate, mannitol, microcrystalline cellulose, povidone, pregelatinized starch, propylene glycol, sodium starch glycolate, and talc.

6.1.3 Combination of Aspirin and Zileuton

No IND is required for this combination of marketed drugs.

6.2 Reported Adverse Events and Potential Risks

6.2.1 Aspirin

Aspirin has been associated with gastrointestinal (GI) side effects. GI side effects include stomach pain, heartburn, nausea, vomiting, and gross GI bleeding. Minor upper GI symptoms, such as dyspepsia, are common and can occur anytime during therapy. Aspirin has also been associated with elevated hepatic enzymes, blood urea nitrogen and serum creatinine, hyperkalemia, proteinuria, and prolonged bleeding time.

6.2.2 Zileuton

Zyflo CR™ has been evaluated in two safety studies. In a 12-week study in patients with asthma receiving 1200 mg bid (n=199) or placebo (n=198), the most frequently reported adverse effects (AEs) were sinusitis (6.5%), nausea (5%), and pharyngolaryngeal pain (5%).^{37, 38} Less common side effects in <1% of treated patients included GI disorders (upper abdominal pain, diarrhea, dyspepsia, vomiting), rash, hypersensitivity, and hepatotoxicity. In the zileuton group, elevated alanine aminotransferase (ALT) levels three times the normal limits occurred in 2.5% (5 of 199) of patients compared to 0.5% (1 of 198) in the placebo group. Most (60%) ALT elevations were reported in the first month of treatment; however, increased ALT was detected 14 days after completing three-months of zileuton treatment in two of the five patients.

Comparable AEs were reported in over 900 patients given 1200 mg Zyflo CR™ bid (n=619) or placebo (n=307) for six months.^{37, 39} Other reported side effects included headache, upper respiratory tract infection, myalgia, and diarrhea. Incidences of low white blood cell (WBC) counts were reported in 2.6% (15 of 619) of zileuton-treated patients and in 1.7% (5 of 307) of placebo-treated patients; all WBC levels returned to normal or baseline upon discontinuation of treatment. Increased liver ALT levels were observed in 1.8% of zileuton-treated patients *versus* 0.7% in placebo. As in the 12-week study, the majority (82%) of ALT elevations occurred within the first three months of treatment and resolved within 21 days of zileuton discontinuation. No cases of jaundice, chronic liver disease, or death were reported due to hepatotoxicity from Zyflo CR™. In

contrast, several cases of death and life-threatening hepatic injury, hyperbilirubinemia, jaundice, and increases in ALT greater than eight times the upper limit of normal were reported in patients taking the discontinued zileuton immediate-release tablet formulation (Zyflo R) during the post-marketing period.³⁷ Since zileuton is contraindicated in subjects with active or acute liver disease, and in those who consume large quantities of alcohol, liver enzyme function tests will be performed prior to randomization in this study.

Zileuton has been shown to decrease the clearance of theophylline and antipyrine, possibly by inhibiting hepatic CYP1A2.³⁷ Likewise, concomitant administration of zileuton and warfarin in normal male adults increased warfarin plasma concentrations and increased prothrombin times; therefore, careful monitoring of prothrombin times is recommended with concurrent therapy. Co-administration of zileuton with propranolol significantly increased propranolol concentrations and increased β -blockade, producing a reduction in heart rate. Such patients require careful monitoring; a dose reduction of propranolol may also be required. Whether zileuton interacts with other β -adrenergic blocking drugs is unknown; no formal studies have been carried out to date.

No significant drug interactions occurred in healthy subjects given zileuton immediate-release tablets (Zyflo R) and naproxen, digoxin, phenytoin, or sulfasalazine.³⁷ Likewise, no drug interactions were observed in studies of healthy volunteers administered zileuton immediate-release tablets concurrently with ethinyl estradiol or prednisone, drugs known to be metabolized by the CYP3A4 isozyme.

6.2.3 Combination of Aspirin and Zileuton

No combination studies of aspirin and zileuton have been reported. Co-administration of aspirin (294 mg/kg-diet) with A-79175 (75 mg/kg diet), a 5-LOX inhibitor structurally related to zileuton, did not produce any gross pathological changes in the liver, kidney, stomach, intestines, or lungs of mice following 25 weeks of treatment.¹¹

There are no published human safety data concerning the concomitant use of aspirin and zileuton in healthy individuals, although no pharmacokinetic or pharmacodynamic interactions were observed in a published study of 24 healthy volunteers co-administered the mixed COX-1/COX-2 inhibitor naproxen (500 mg) and zileuton (800 mg).⁴⁰ The drug combination had no effect on plasma concentration-time curves when compared with either agent given alone. Moreover, there was no evidence the drug combination altered serum LTB₄ or thromboxane B₂ levels beyond that observed with either naproxen or zileuton alone. Blockade of 5-LOX did not produce additive GI AEs typically associated with naproxen administration. This is in agreement with reports of reduced GI toxicity associated with dual COX/5-LOX inhibitors such as licofelone.^{41, 42} Given these data, the risk of GI toxicity resulting from the combined administration of aspirin and zileuton appears to be low. The possibility of additive hepatic toxicity from the combined use of aspirin and zileuton cannot be completely ruled out since both drugs are metabolized by the liver.

6.3 Availability

Aspirin 81 mg and placebos for both aspirin and zileuton will be supplied to investigators by NCI, DCP. Zileuton will be ordered by the institutional pharmacy.

6.4 Agent Distribution

Agents will only be released by NCI, DCP after documentation of IRB approval of the DCP-approved protocol and consent is provided to DCP and the collection of all Essential Documents is complete (see DCP website for description of Essential Documents).

NCI, DCP-supplied agents may be requested by the Investigator (or their authorized designees) at each Organization. DCP guidelines require that the agent be shipped directly to the institution or site where the agent will be prepared and administered. DCP does not permit the transfer of agents between institutions (unless prior approval from DCP is obtained). DCP does not automatically ship agents; the site must make a request. Agents are requested by completing the DCP Clinical Drug Request form (NIH-986) (to include complete shipping contact information) and faxing or mailing the form to the DCP agent repository contractor:

[name]
MRIGlobal
DCP Repository
[name]

[name]
[contact]
[contact]
Email: [contact]
Emergency [contact]

6.5 Agent Accountability

The Investigator, or a responsible party designated by the Investigator, must maintain a careful record of the inventory and disposition of all agents received from DCP using the NCI Drug Accountability Record Form (DARF). The Investigator is required to maintain adequate records of receipt, dispensing and final disposition of study agent. This responsibility has been delegated to the University of Arizona Cancer Center (UACC) Research Pharmacy Staff. Include on receipt record from whom the agent was received and to whom study agent was shipped, date, quantity and batch or lot number. On dispensing record, note quantities and dates study agent was dispensed to and returned by each participant.

6.6 Packaging and Labeling

Aspirin, aspirin placebo and zileuton placebo will be packaged and shipped by the NCI, DCP drug repository to the UACC research pharmacy. Zileuton will be ordered by the UACC research pharmacy who will re-package the zileuton in empty bottles supplied by DCP drug repository. Lot numbers will be captured in the research pharmacy's repackaging records with the participant ID and randomization number for traceability.

6.7 Storage

Study agents will be stored in a secure location at temperatures between 15°C and 30°C (59°F and 86°F).

6.8 Registration/Randomization

Participants will be randomized to receive ASA 81 mg QD + zileuton (Zyflo CR™) 2 x 600 mg BID or double placebo for three months.

Participants will be considered registered on the date they sign the approved informed consent document with a member of the study staff. The study coordinator will contact the UAZ Consortium Office for a subject number when the subject has been consented. See section 13.2 for details of the study randomization procedures.

